The survey instruments will not be audio or video recorded.

We will attempt to align these three visits with the participants’ usual care visits.

Intervention: Decision-Aid for Renal Therapy (DART) is an interactive, web-based decision-aid intended to facilitate shared decision-making among patients, caregivers, and clinicians. DART was designed using a rigorous scientific process with input from patients, clinicians, researchers, and health communication experts and has received the highest scores of any Chronic Kidney Disease (CKD) decision aid by International Patient Decision Aid Standards (IPDAS). DART is accessible on devices (smart phones, tablets, computers) that many patients and caregivers already own or that will be made available to patients in a private setting in clinics. DART is designed to be accessible to diverse populations, including older adults with chronic conditions, persons residing in rural areas, and persons of varying socioeconomic backgrounds. *A significant advantage of decision-aids is their ability to be disseminated and implemented rapidly, potentially improving clinical practice and patient and caregiver outcomes.* Participants who engage with DART watch an approximately 30-minute interactive video that explains treatment options for kidney failure and the benefits and risks of different treatment options. Participants have the opportunity to make notes while using the program and to print out questions and information from the program. DART administration is not part of usual care for chronic kidney disease patients at Tufts Medical Center.

Administering DART and training. Participants randomized to DART will access DART during their first visit, which will take approximately 90 minutes (60 minutes for an interview and 30 minutes to interact with DART). Participants will interact with DART (use the program to learn about kidney disease treatments and understand the benefits and risks of different treatment options) in the clinic. A research assistant will help participants access and navigate DART on a tablet or desktop computer in the clinic. Patients and caregivers can complete DART together or separately. Participants will also receive an email link to DART if they wish to access it from their own tablet or computer at home.

Participants randomized to DART can continue to access DART from home throughout the duration of the trial.

Participants randomized to DART will also receive Usual Care.

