Usual Care Comparator: Comparative effectiveness trials seek to compare two alternate therapeutic approaches. In this case, *usual care (UC) is the most appropriate comparator because it represents the clinically relevant alternative treatment that patients and their caregivers are most likely to experience in current practice.* =

There is no current standard for pre-dialysis education, although the Centers for Medicare and Medicaid Services (CMS) reimburse chronic kidney disease education. All participants receive *both printed and e-mailed electronic* versions of 'Choosing a Treatment For Kidney Failure' https://www.kidney.org/sites/default/files/11-10-0352_choosing_treat.pdf, written and published by the National Kidney Foundation, and commonly provided in current practice. By providing identical written materials describing treatment options in a balanced and fair way to all patients at the first study visit following randomization, we minimize content heterogeneity and bias associated with timing and setting. As part of assessments, we will query participants in both study arms regarding participation in dialysis education sessions.

DART will not be administered to participants in the usual care group.

Laboratory tests: We will not conduct laboratory tests for this study. We will assess medical records for the following laboratory tests conducted as part of usual care for chronic kidney disease: serum creatinine (which is used to calculate glomerular filtration rate, or GFR), calcium, phosphate, bicarbonate, albumin, hemoglobin, urine albumin, urine protein and urine creatinine.

1. **Study Procedures:** Eligible participants will be approached and, if interested, the study coordinator or trained research staff will obtain informed consent at Tufts Medical Center. [name], the St. Elizabeth's Medical Center Principal Investigator, will screen eligible patients and oversee consent of interested patients at St. Elizabeth's Medical Center. Eligible patients from St. Elizabeth's Medical Center will first give [name] permission to be contacted about the study, including being approached for consent, by Tufts research staff.

After providing consent, participants (patient-caregiver dyads) will be randomized to one of two study groups using REDCap. One group will receive usual care, and the second group will receive usual care plus DART. Participants in both study groups will complete three visits to the clinic:

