Visit 1 (60 minutes for participants in the usual care group; 90 minutes for participants in the DART study group)

A research team member will ask questions about the participant's experiences making decisions about kidney disease and treatment, or helping a loved one make decisions about kidney disease and treatment. Participants who are assigned to receive regular care will receive a printed educational pamphlet, "Choosing a Treatment for Kidney Failure," published by the National Kidney Foundation. Participants who are assigned to DART will receive the educational pamphlet and will also have the opportunity to complete DART in the clinic setting. A research assistant will help participants access and navigate DART on a tablet or desktop computer in the clinic. Patients and caregivers can complete DART together or separately. Participants will also receive an email link to DART if they wish to access it from home.

Visit 2 (30 minutes). This visit will take place three months after Visit 1.

Participants in both study groups will be asked questions about their experiences making decisions regarding kidney disease treatment, their goals of medical care, and views about their health.

Visit 3 (30 minutes). This visit will take place six months after Visit 1.

Both sets of participants will be asked questions about their experiences making decisions regarding kidney disease treatment, their goals of medical care, and views about their health.

We will attempt to align these three visits with the participants' usual care visits.

Caregiver interviews will be conducted in-person at the clinic if they are accompanying the patient, or will be done by mail or phone. The caregiver will be given an addressed, stamped envelope in which to mail the survey back.

2. Subject Timeline:

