Alternative strategies will include the Tufts CTSI to query the Tufts MC EHR for individuals age 70+, eGFR between 10 and 30, and a relationship with an outpatient provider affiliated with Tufts Medical Center. Using this list, coordinators will further screen for eligibility, including use of the kidney risk failure equation and evaluate notes for patient awareness of their chronic kidney disease. If aware of kidney disease and eligible, opt-out letters (Appendix 2) will be sent to participants followed by a phone call 1 weeks later.

Patients will be asked to identify a primary caregiver/care partner with whom they discuss important matters and who would be most likely to make a decision for them in the case that they could not decide or communicate their wishes. The term caregiver does not imply that the patient requires immediate fulltime care, but rather refers to the individual most likely to participate in decision-making and assistance with daily living. If the primary caregiver is accompanying the patient, the caregiver will also be approached after the patient has consented. The study will be explained to the caregiver, and the caregiver will be given the opportunity to consent to the study. If a caregiver is not accompanying the patient, we will ask the patient to identify a primary caregiver and for the caregiver's contact information. A recruitment/opt-out letter will be sent to the caregiver, followed by a phone call 1 week later, to ask if s/he is interested in enrolling and to schedule a time for him/her to come into the clinic to consent for the study if interested.

A patient does not need a caregiver to participate in the study.

The recruitment/opt-out letter (patient and caregiver), scripts for phone calls, and flyer are attached to this application.

2. **Registration:** Patient and caregiver participant who have consented will be given unique identifiers after randomization. Patient-caregiver pairs (dyads) will receive either DART or usual care,

with randomization blocked by study site using blocks of randomly varying size using RedCap. Nephrologists will become aware of the randomization outcomes immediately prior to the clinic visit, as patients will bring with them a printed copy of their preferences and questions about treatment (an outcome of the DART). The unique participant identifiers will be used on all materials and survey forms following randomization.

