At the baseline visit, following consent and randomization, patients randomized to DART will receive usual care plus an email with a unique link to DART. During the baseline visit after completion of baseline surveys, a research team member will guide patients and caregivers randomized to DART on how to access and navigate DART on a tablet or desktop and how to print question prompts to facilitate discussions with their clinical team. This training will take approximately 15 minutes. To increase generalizability, we accommodate participants who do not currently have internet access by using web-enabled tablet set-up in a quiet, private room at the clinic to access DART. Participants will receive a phone number to reach research team members for questions.

3. **Screening Interview/questionnaire:** A screening script will not be used. The scales and questionnaires are provided as Appendix 1.

We will not be audio or video recording the survey instruments.

Construct	Measure	Month		
		0	3	6
Patient Assessments				
Decisional Capacity	Decisional Conflict Scale	x	x*	x
Advanced Care Planning	Completion of Advanced Directive	x	x*	x
Health related quality of life	KDQOL-36	x	x	
Cognitive Function	Montreal Cognitive Assessment	x		
Patient and Caregiver Assessments				
Concordance	Goals of Care Document		x*	
Satisfaction with Care	CANHELP Lite Questionnaire	x	x*	
Satisfaction with Life	Satisfaction with Life Scale	x	x	x
Depression	CESD-R	x		x
Anxiety	Hospital Anxiety and Depression Scale †	x		x
Caregiver Assessments				
Caregiver Burden	Caregiver Burden Scale	x	x*	x

4. **Transportation:** Interviews and surveys will be administered during regular clinical visits. In the case that a patient or caregiver prefer to complete the survey outside the clinic at our research lab at [name], we will provide a \$5 transportation stipend and free parking.

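### The month-0 decisional conflict score and directive status are collected after randomisation with nothing hiding the arm; complete both before the allocation is made or revealed.

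*Protocol*

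**What the plan says.** **Order of events.** Protocol, Study Procedures: "After providing consent, participants (patient-caregiver dyads) will be randomized to one of two study groups using REDCap". The visits are described after that: "Participants in both study groups will complete three visits to the clinic". Usual Care Comparator says that the pamphlet goes "to all patients at the first study visit following randomization". Section III.G.2 (Registration) has: "At the baseline visit, following consent and randomization, patients randomized to DART will receive usual care plus an email".

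**Visit 1 differs by arm.** Study Procedures gives: "Visit 1 (60 minutes for participants in the usual care group; 90 minutes for participants in the DART study group".

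**Surveys and DART.** Registration puts guided use of DART after the surveys: "During the baseline visit after completion of baseline surveys, a research team member will guide patients and caregivers randomized to DART". On the emailed link, Administering DART and training says: "Participants will also receive an email link to DART if they wish to access it from their own tablet or computer at home".

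**Identifiers.** Registration: "Patient and caregiver participant who have consented will be given unique identifiers after randomization". These identifiers then label the survey forms.

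**Pamphlet.** The Visit 1 description for the usual care group, under Specific methods and techniques, lists the pamphlet before the questions. The Visit 1 description under Study Procedures lists the questions first.

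**Measures and their use.** The assessment table schedules the DCS and directive completion at month 0, both as patient assessments. The confidentiality section has research assistants administer the paper surveys. The SAP names the three-month DCS as a co-primary outcome and analyses it by linear regression with baseline DCS as covariate. The first of its two secondary directive analyses drops patients who already had a directive at baseline.

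**The concern.** Adjusting for a baseline value is safe when allocation cannot have affected that value. Here the baseline is a self-report taken after the arm has been drawn, at a visit whose planned length already depends on the arm, and nothing keeps the arm from the patient or from the person administering the form. If either knows it, the answers could shift. The covariate would then carry part of the effect of allocation, and the regression would subtract it from the estimated difference.

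The directive exclusion has the same weakness: it selects patients on a status recorded after randomisation, so the patients left in the two arms need not be comparable. I would expect a completed form to move less than a conflict score, but the plan gives no assurance for either. The data collected could not show afterwards whether a baseline had moved. One of two co-primary comparisons and one secondary analysis are at stake.

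**Working it through.** **1. Sequence.** Study Procedures gives consent, randomisation, then three visits. Usual Care Comparator makes Visit 1 the visit that follows randomisation. Registration has participants already randomised at the baseline visit and places the baseline surveys within it. The arm-specific visit lengths fit this order. No section puts the month-0 DCS before the REDCap draw.

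**2. Routes by which the baseline could move.**
- Guided DART use: closed, because it follows the surveys.
- Emailed link: its timing relative to the surveys is not stated, but it is sent at the baseline visit and meant for home use, so early use by the patient is unlikely.
- Pamphlet: both arms receive it, so it matters between arms only if its place in the visit differs by arm in practice. The two Visit 1 descriptions disagree on the order.
- Knowledge of the arm: open. The documents do not say when patients are told.

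**3. Illustrative size.** The plan gives no DCS standard deviation, slope or expected shift, so it has no figure to reproduce.
- From the Protocol: 31 patients, taken as 15 v 16 (equal allocation assumed).
- Assumed: baseline shift d in one arm; within-arm slope b of three-month on baseline DCS; fraction p of the shift that persists at three months. All are in SD units, so b is also the correlation.

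With true effect T, the three-month difference is T + p × d and the baseline difference is d. The adjusted estimate is therefore T + p × d − b × d.

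If the target is the effect of assignment including awareness, T + p × d, the error is −b × d whatever p is:
- d = 0.2, b = 0.5: −0.10 SD
- d = 0.2, b = 0.7: −0.14 SD
- smallest over d = 0.1 to 0.3: 0.1 × 0.5 = 0.05 SD in size
- largest: 0.3 × 0.7 = 0.21 SD in size

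A simulation of 20,000 trials per setting (15 v 16, d = 0.2) gave −0.100 and −0.140 for b = 0.5 and 0.7, at p = 0, 0.5 and 1.

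Standard error = √[(1 − b²)(1/15 + 1/16)]:
- b = 0.5: √(0.75 × 0.1292) = 0.311
- b = 0.7: √(0.51 × 0.1292) = 0.257

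The ratios are 0.10/0.311 = 0.32 and 0.14/0.257 = 0.55, or 0.31 and 0.53 with the simulated standard errors of 0.319 and 0.263.

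**4. The other target.** If the target is T alone, free of awareness, the deviation is (p − b) × d as written and p × d with a pre-allocation baseline. For d = 0.2:

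| p | As written, b = 0.5 | As written, b = 0.7 | Pre-allocation baseline |
|---|---|---|---|
| 0 | −0.10 | −0.14 | 0 |
| 0.5 | 0 | −0.04 | 0.10 |
| 1 | 0.10 | 0.06 | 0.20 |

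The as-written deviation is the smaller whenever p > b/2, which covers four of these six settings.

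**5. Dropping the covariate instead.** This also avoids the −b × d error, but the standard error becomes √(1/15 + 1/16) = 0.359 SD rather than 0.257 to 0.311 SD.

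**The case against.** The strongest reply is that the plan states no unsafe procedure. Randomising before a survey does no harm unless the arm is known, and the documents are silent on when it is revealed. The Registration sentence about guiding DART participants after the surveys is itself a safeguard. The sentence that places the baseline visit after randomisation dates the email, not the DCS. All of this stands, and it limits the point to a protection that is not assured. It does not alter the order given in Study Procedures and Usual Care Comparator.

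A second reply also stands in part. On a target that excludes awareness, the two biases can partly cancel, and moving the baseline can enlarge the total deviation. The SAP does not say which target it intends. But that cancellation depends on three unknown quantities and cannot be relied on, whereas a pre-allocation baseline gives a clean estimate of the effect of assignment.

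A reader might infer that DART content contaminates the baseline. The documents do not support that: guided use follows the surveys and the link is for home use. A reader might also infer a badly inflated false-positive rate. With 31 patients and no persistence, simulation (4,000 runs per setting) gave about 6% and 8% at a shift of 0.2 SD for b = 0.5 and 0.7. It reached 24% only with an assumed shift of 0.5 SD and slope 0.7, and nothing in the documents supports a shift of that size.

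**Conclusion.** The point holds at low severity. As written, the month-0 DCS and directive status are taken after randomisation with no step that hides the arm, and the SAP uses both in ways that assume allocation has not touched them. That patients or research assistants know the arm by then is an inference.

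For the effect of assignment including awareness, the illustrative error is 0.10 to 0.14 SD, roughly a third to a half of a standard error, given d = 0.2 SD, b = 0.5 to 0.7 and 15 v 16 patients. None of d, b or p comes from the documents, and the direction of any shift is unknown. It would be wrong to conclude that the co-primary comparison is biased; the plan only fails to rule that out.

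The consequence is limited. The Protocol's Outcome section makes feasibility and usability the main outcomes, Aim 2 lists decisional conflict as secondary, and the SAP says the trial lacks the power to establish efficacy.

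**What to change.** In Specific methods and techniques (Visit 1), Usual Care Comparator, Study Procedures including its Visit 1 description, and Registration, state that the patient's month-0 DCS and directive status are completed after consent, before the REDCap allocation is made or revealed, and before the pamphlet or DART link is given. Make the two Visit 1 descriptions agree on where the pamphlet comes. Issue the study identifier at consent so that these forms can be labelled. Do not delay randomisation for an absent caregiver.

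The cost is Protocol wording and a small reordering of steps within Visit 1; sample size, instruments and number of visits do not change. There are two downsides. The 90-minute slot may have to be held for every patient, because the arm would not be known when the visit is booked. Some caregivers will also have no pre-randomisation baseline, although the DCS analysis uses patient data only. The change does not remove any effect of knowing the arm on the three-month score.

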Successful recruitment is the major challenge of all clinical trials, although the sample in this pilot does not pose a significant challenge based on current population estimates of potentially eligible participants using local electronic health records. Recruitment barriers will be overcome by several approaches including: 1) personal outreach from treating physicians; 2) information sessions and individual meetings with clinic staff at participating clinics; and 3) written communication and follow-up telephone calls. Recruitment strategies are designed to minimize respondent burden. Should recruitment be below target, alternative strategies described below will be implemented within 3 months of starting recruitment.

- 14. How new information will be conveyed to the study subject and how it will be documented:** New information will not be conveyed to study subjects.

- 15. Payment, including a prorated plan for payment:** Participants (each patient and caregiver in both study groups) will be offered a \$25 gift card after completing the first visit, and an additional \$15 gift card for each of the subsequent two follow-up visits, for a total of \$55 for completing the entire study. In the case that a patient or caregiver prefers to complete the survey outside the clinic at our research lab at [name], we will provide a \$5 gift card as a transportation stipend. We will use a participant payment log (attached in this amendment) to keep track of gift card disbursement. Participants will fill in the top half of the form (name, social security number, and address) after providing informed consent. The remainder of the form (gift card amount, date gift card distributed, and participant signature) will be completed after the participant receives the gift card.

- 16. Payment for a research-related injury:** none

- I. Outcome:** This is a pilot study, and as such, our main outcomes are feasibility of the study design and recruitment, and usability of the intervention. Nonetheless, we estimate that patients who will be exposed to DART will be more likely to complete advance care plans, they will be more satisfied with their decisions and better informed of their treatment options. We also hypothesize that their caregivers will be more likely to know patients' preferences for care.
- J. Tissue banking considerations:** none

VULNERABLE POPULATIONS: Not recruiting children, prisoners, pregnant women, or persons with dementia, all of whom would be ineligible to participate.

Study: Decision-Aid for Renal Therapy Pilot Trial (DART Pilot Trial)

NCT Number: not yet assigned

Date of document: 2/20/2018

Primary Outcomes:

1. Completion of advance directives.

The primary outcome of this pilot trial is completion of advance directives at 3 months, which will be the first study visit after administration of the educational instrument.

2. Decisional conflict

The other primary outcome of this pilot trial is the difference in the decisional conflict scale score at 3 months, which will be the first study visit after administration of the educational instrument.

Statistical Analysis Plan:

Co-primary outcomes in this pilot trial include completion of advance directives at three months and changes in decisional conflict score at three months. For completion of advance directives, we will use logistic regression, dichotomizing advance directives as completed or not completed at the three month visit. There will be two secondary analyses of advance directives; the first will exclude anyone with completed advance directives at baseline from analyses while the second will look at any completion versus non-completion prior to death or a terminal hospitalization, extending beyond the initial three month follow-up. Advance directives can include DNR/DNI forms as well as completion of the Massachusetts Orders for Life-Sustaining Treatment (MOLST), a local Physician Orders for Life-Sustaining Treatment (POLST) equivalent.

The primary analysis for DCS will be a comparison between study arms at 3 months, using linear regression to adjust for baseline DCS. In secondary analyses, leveraging longer term data, all post-baseline measurements of DCS over time will be analyzed together in a single linear mixed effects model to account for within patient correlation.

Secondary outcomes will be analyzed similar to advance directives if dichotomous or similar to the DCS if continuous and are hypothesis generating for future trials. Critically, this pilot trial is not sufficiently powered to conclude efficacy of the DART survey instrument but rather is designed for feasibility assessment.

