- a) *Inclusion criteria: CKD stages 4 or 5 (non-dialysis); 2) Age >=70; 3) English speaking; 4) willingness to be randomized to DART, and (5) able to sign informed consent, (6) Kidney Failure Risk Equation greater than 15% risk using [www.kidneyfailurerisk.com], (7) GFR<30*
- b) *Exclusion criteria: Non-English speaking patients will be excluded from this study because DART is an online educational program that is only available in English at this time.*
- c) *Withdrawal/Termination criteria: Death, withdrawal of consent, censoring for study end*

D. **Risk/benefit assessment:** This study does not pose more than minimal risk.

- 1. **Physical risk:** None
- 2. **Psychological risk:** Participants could experience mild discomfort with the survey questions or with the DART educational intervention. This risk is no greater than minimal risk, and participants can withdraw at any time.
- 3. **Social risk:** Risk of loss of confidentiality.
- 4. **Economic risk:** None
- 5. **Benefit of participating in the study:** There is no direct benefit to participants. However, there is a potential for improving communication between clinicians, patients, and family members. An additional benefit is the potential for greater concordance

between patient values and treatment selection.

Specific methods and techniques used throughout the study: The control group will receive usual care from their health care team for their chronic kidney disease. Following consent, participants (patient-caregiver dyads) randomized to usual care will participate in three visits to the clinic:

Visit 1 (60 minutes)

Participants will be given an education pamphlet, “Choosing a Treatment for Kidney Failure,” published by the National Kidney Foundation. A research team member will ask questions about the participant’s experiences making decisions about kidney disease and treatment, or helping a loved one make decisions about kidney disease and treatment.

Visit 2 (30 minutes). This visit will take place 3 months after visit 1.

Participants will be asked questions about their experiences making decisions regarding kidney disease treatment, their goals of medical care, and views about their health.

Visit 3 (30 minutes). This visit will take place 6 months after visit 1.

Participants will be asked questions about their experiences making decisions regarding kidney disease treatment, their goals of medical care, and views about their health.

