Participants will be recruited over 10 months in 2 centers in Greater Boston (TMC and St. Elizabeth's Medical Center, a Tufts teaching affiliate in Brighton). This will allow a sufficient population to meet recruitment targets while ensuring a diverse sample, including understudied populations known to experience a greater burden of symptoms and greater difficulty in decision-making. Specific factors of interest include: race, ethnicity, and socioeconomic status. Patients and caregivers from these sites have expressed interest in participating in this study. St. Elizabeth's is a Tufts University School of Medicine (TUSM) teaching hospital and a partner in the Tufts Clinical and Translational Science Institute (CTSI); multiple clinical and research collaborations are ongoing between TMC and SEMC.

Follow-up time will be 6 months, with follow-up interviews conducted at 3 months and 6 months after the baseline visit.

F. Assessment of Subject Safety and Development of a Data and Safety Monitoring Plan

1. Definition of Serious Adverse Event (SAE) and Adverse Event (AE) for this study: Although none are anticipated, during the course of a research study, unanticipated problems involving risk to subjects or others, non-compliances, and other events may occur that need to be reported to the IRB in accordance with 45 CFR 46.103(b)(5) and 21 CFR 56.108(b). We will follow the Tufts IRB Reportable New Information Policy. For this study, the intervention consists of patients and care partners receiving access to and viewing a decision-aid program that contains educational material about chronic kidney disease and treatment options. Receipt of access to this program and use of the program is intended to better inform patient of their options and prompt patients to raise questions with physicians about their future treatment options. The decision-aid should not interfere in any way with the patient-provider relationship. The decision-aid is not intended to influence the treatment options that patients select. Whether the patient has a medical event (e.g. dialysis initiation) is not an adverse event related to the study. Therefore, although we will collect data related to treatment choices, the intervention does not directly impact these choices, and therefore this study does not require a data safety plan.
2. Reporting timeframe for SAEs and AEs: n/a
3. Accountability procedures as they relate to drugs, devices, and data: n/a

G. Subject Participation

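### Cheap improvement, low severity: take the primary month-3 DCS contrast from a repeated-measures model, so that patients who miss month 3 but attend month 6 still contribute

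*SAP*

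**What the plan says.** The SAP gives DCS co-primary status: "Co-primary outcomes in this pilot trial include completion of advance directives at three months and changes in decisional conflict score at three months". Its primary analysis is a single-visit regression: "The primary analysis for DCS will be a comparison between study arms at 3 months, using linear regression to adjust for baseline DCS". Longer-term data enter only in a secondary analysis, where "all post-baseline measurements of DCS over time will be analyzed together in a single linear mixed effects model to account for within patient correlation". No arm-by-visit term is stated for that model, and no month-3 contrast is named from it.

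In the protocol, the assessment table (section III.G.3) lists the "Decisional Conflict Scale" at months 0, 3 and 6, and Subject Timeline confirms the visits: "Follow-up time will be 6 months, with follow-up interviews conducted at 3 months and 6 months after the baseline visit". Study Procedures says of timing "We will attempt to align these three visits with the" participants' usual-care appointments. The withdrawal and termination criteria (III.C.1) are "Death, withdrawal of consent, censoring for study end".

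Neither document gives an expected dropout rate, a missing-data rule, an analysis population or a sensitivity analysis for missing DCS scores. Retention is itself a feasibility outcome (Aim 1D).

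**The concern.** A patient without a month-3 score has no outcome value for the primary regression, so standard fitting leaves that patient out even when a month-6 score exists. Patients are aged 70 or over with advanced kidney disease, and visit timing depends partly on clinic scheduling, so a missed Visit 2 followed by an attended Visit 3 is a foreseeable pattern. With 31 patients enrolled, each omission is 1/31, about 3% of the data.

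Two things are at stake: some precision, and protection against bias if the patients who skip month 3 differ in DCS in one arm but not in the other. The month-6 score carries information on both, and it is collected anyway.

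**Working it through.** **Figures in the plan.** There is none to reproduce for DCS: no standard deviation, effect size, power or dropout rate is given. The 31 comes from the advance-directive calculation and is used here only as the number enrolled.

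**Assumed inputs.** Correlation of each follow-up score with baseline 0.5; month-3/month-6 correlation *r* = 0.5 to 0.75; 10-20% missing month 3; 50-70% of those attending month 6; equal allocation (15 v 16). In the simulations at *r* = 0.75 the true effect is -0.50 SD.

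**Complete data.** If both visits share the same covariates (arm and baseline, each crossed with visit) and the covariance is unstructured, the joint model's month-3 arm coefficient equals the regression coefficient. On a complete simulated data set both gave -0.7213. The two also coincide when nobody who misses month 3 returns at month 6.

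**Precision.** Let *o* be the fraction with a month-3 score, *e* the fraction with a month-6 score only, and ρ the month-3/month-6 correlation given baseline. In large samples, with month 6 complete among month-3 attenders,

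variance ratio (joint / regression) = 1 - ρ² × *e*/(*o* + *e*), with ρ = (*r* - 0.25)/0.75.

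So *r* = 0.5 gives ρ = 0.33 and *r* = 0.75 gives ρ = 0.67.

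- 10% missing, 50% return, *r* = 0.5: 0.111 × 0.05/0.95 = 0.006, a fall of 0.6%.
- 20% missing, 50% return, *r* = 0.5: 0.111 × 0.10/0.90 = 0.012, a fall of 1.2%.
- 10% missing, 70% return, *r* = 0.75: 0.444 × 0.07/0.97 = 0.032, a fall of 3.2%.
- 20% missing, 70% return, *r* = 0.75: 0.444 × 0.14/0.94 = 0.066, a fall of 6.6%.
- Nobody returns: *e* = 0, no gain.

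Simulation with 15 v 16 patients and missingness unrelated to DCS gave ratios of about 0.92-0.96 at *r* = 0.75 and near 1.0 at *r* = 0.5. Together these give a fall of about 0-8%. In patients: at ρ = 0.5 with half returning, the gain is worth about 0.4 (10% missing) to 0.7 (20% missing) of 31.

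**Bias.** Simulated mean month-3 contrast at 20% missing, truth -0.50 SD:

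| Why month 3 is missing | Regression | Joint model |
|---|---|---|
| Follows month-6 DCS, DART arm only | bias -0.11 | bias -0.03 |
| Follows month-6 DCS, same link in both arms | -0.494 | -0.495 |
| Follows the unseen month-3 DCS, DART arm only | -0.647 | -0.602 |
| At random, but return at month 6 selective in the DART arm | -0.506 | -0.531 |

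Row 1: (0.11 - 0.03)/0.11 = 73% of the bias is removed. Row 2: neither estimate is biased. Row 3: bias falls from 0.147 to 0.102, so 0.045/0.147 = 31% is removed. Row 4: the joint model is shifted by 0.031 and the regression by 0.006.

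A separate run of the row 1 mechanism, with ρ = 0.5, 31 patients and no true effect, gave -0.078 v -0.031 if half return, -0.096 v -0.014 if all return, and identical values if none return.

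**The case against.** The strongest reply is that nothing here is wrong as planned. Baseline-adjusted regression at the target visit is a standard primary analysis and matches the stated month-3 outcome. A patient seen only at month 6 is already used in the planned secondary model. The trial is a feasibility pilot that the SAP says is not powered to conclude efficacy. The standard error in these simulations is about 0.36 SD. Even when DART-arm missingness follows the month-6 score, one simulation put the fall in root-mean-square error at only 0.371 to 0.352. All of this stands, and it is why the severity is low.

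Four stronger readings are tempting and are not supported:

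- *The SAP has a rule that drops these patients.* It has no such rule. The omission is the default behaviour of the named method, in a plan that is silent on missing data.
- *The regression is biased whenever missing month 3 is related to DCS.* Not for the arm contrast: with the same link in both arms there was no bias.
- *The change cannot hurt.* This holds for complete data. With selective return at month 6 the joint estimate shifts slightly, although its overall error was still slightly lower in that setting.
- *The model is already planned, so only the labels need swapping.* Without an arm-by-visit term, that model would estimate an average effect over months 3 and 6.

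Aligning visits with usual care could equally improve attendance, so it shows only that intermittent missingness is possible.

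**Conclusion.** The point holds as a modest, nearly free improvement and not as an error. The primary DCS analysis by default ignores month-6 information from patients who miss month 3, and a joint model would use it for the same month-3 contrast. Its overall error was lower or about equal in every simulated setting.

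The size rests wholly on assumed missingness and correlations: about 0-8% lower variance, and partial to substantial removal of a bias that exists only if the missingness link differs by arm. A reader might infer that the change solves missing DCS data in this trial. It does not: patients who die or withdraw before month 3 have no post-baseline score and are left out of both models.

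**What to change.** In the SAP, define the primary DCS estimate as the month-3 arm contrast from one repeated-measures model of the month-3 and month-6 scores. Specify arm-by-visit and baseline-DCS-by-visit terms, unstructured covariance, REML and Kenward-Roger degrees of freedom, and include every randomised patient with any post-baseline DCS. Keep the month-3 linear regression as a sensitivity analysis.

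State the missing-data assumption in the same place: missing scores are explained by arm, baseline DCS and the other observed score. Say separately how patients with no post-baseline DCS will be reported.

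The cost is a sentence or two and no new data. The downsides are reliance on that assumption, a possible slight shift if return at month 6 is selective, and the need for small-sample degrees of freedom with about 31 patients.
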